3.0 Introduction

This statistical analysis plan (SAP) describes the statistical analyses to be completed by the Data and Statistical Science Department for ABBV-066 Study M15-989. It provides details to further elaborate statistical methods as outlined in the protocol and describes analysis conventions to guide the statistical programming work.

Unless noted otherwise, all analyses will be performed using SAS version 9.2 or later (SAS Institute Inc., Cary, NC 27513) under the UNIX operating system.

4.0 Study Background

4.1 Objectives

The purpose of this long-term safety extension trial is to provide patients who responded to treatment with BI 655066/ABBV-066 (risankizumab) in a preceding trial with a long-term treatment option.

The primary objective of the study is to investigate long-term safety of BI 655066/ABBV-066 (risankizumab), in patients with moderately to severely active Crohn's disease, who achieved a clinical response or remission on previous treatment with BI 655066/ABBV-066 (risankizumab) and are now receiving long term treatment.

Additional objectives of this study are to further investigate long-term efficacy, tolerability, pharmacokinetics, pharmacodynamics and immunogenicity of BI 655066/ABBV-066 (risankizumab).

4.2 Study Design

This open label long term extension trial investigates the long-term safety and efficacy of BI 655066/ABBV-066 (risankizumab). Approximately 60 patients who met the entry criteria were planned for inclusion in this trial, rolling over from preceding trial Study M15-993/1311.6.

[figure not shown]
All patients directly rolled over from Study M15-993/1311.6 into Study M15-989/1311.20 received 180 mg BI 655066/ABBV-066 (risankizumab) subcutaneously (SC) from Visit 2 onwards every 8 weeks. Patients who lost clinical response or remission after the end of treatment in Study M15-993/1311.6 and/or at screening for Study 1311.20/M15-989 received open label, i.e., re-induction treatment with three intravenous infusions (IV) of 600 mg each every 4 weeks. Patients who complete this study may elect to continue in Study M16-000 Sub-Study 3 (Phase 3 open label extension study).

4.2.1 Study Design and Design Diagram

This trial is a single group, open label extension study of BI 655066/ABBV-066 (risankizumab) in patients with moderately to severely active CD. The patients enrolled in this study are those that achieved clinical response to previous treatment with BI 655066/ABBV-066 (risankizumab).

Patients rolling over from preceding trial Study M15-993 completed Period 2 or 3 in that trial and either demonstrated a clinical response without remission at Visit E1 (Week 26 visit of Period 2) or a clinical response or remission at Visit E5 (Week 52 visit of Period 3) as defined by that protocol (see [Figure 1](#)).

Figure 1. Guideline for rolling over of patients from Study M15-993/1311.6 to long term extension Study M15-989/1311.20.

The scheduled activities during the whole study are shown in Flow Chart 1, Flow Chart 2 and Flow Chart 3 respectively for different types of rolling over.

FLOW CHART 1: PATIENTS (1) ROLLING-OVER AT WEEK 26 FROM PRECEDING TRIAL 1311.6 (WITH CLINICAL RESPONSE BUT NOT REMISSION AT VISIT E1); OR (2) WHO MAINTAINED RESPONSE OR REMISSION AFTER COMPLETION OF TRIAL 1311.6, VISITS 1-18

Trial Period	Screening		Treatment period																
	1 ^{1,2}	1.1 ¹⁵	2	3	4	5	6	7	8	9	10	11	12	13	14	15	16	17	18
Visit			2	3	4	5	6	7	8	9	10	11	12	13	14	15	16	17	18
Week	0	1	4	12	20	28	36	44	52	60	68	76	84	92	100	108	116	124	132
Time window (days)	+5	+5	± 7	±7	±7	±7	±7	±7	±7	±7	±7	±7	±7	±7	±7	±7	±7	±7	±7
Informed consent	X																		
Assessment of eligibility	X																		
LABS/SAFETY ASSESSMENTS																			
Detailed physical examination	X																		
Targeted physical examination (incl. vital signs)			X	X	X	X	X	X	X	X	X	X	X	X	X	X	X	X	X
Weight	X		X	X	X	X	X	X	X	X	X	X	X	X	X	X	X	X	X
12 Lead Resting-ECG	X																		
Urine Pregnancy test ⁴	X		X	X	X	X	X	X	X	X	X	X	X	X	X	X	X	X	X
Laboratory tests (serum chemistry, hematology, urinalysis) ⁹	X		X	X	X	X	X	X	X	X	X	X	X	X	X	X	X	X	X
QuantiFERON-TB Gold In-Tube test ⁵	X								X						X				
EFFICACY ASSESSMENTS																			
Dispense patient diary for screening ³	X																		
Crohn's Disease Activity Index (CDAI), PRO-2	X ¹⁷	X	X	X	X	X	X	X	X	X	X	X	X	X	X	X	X	X	X
Review patient diary	X ¹⁷	X	X	X	X	X	X	X	X	X	X	X	X	X	X	X	X	X	X
Fistula exam	X		X	X	X	X	X	X	X	X	X	X	X	X	X	X	X	X	X
Inflammatory Bowel Disease Questionnaire (IBDQ) ¹³			X			X			X			X			X			X	
Ileocolonoscopy (CDEIS)	X ¹								X							X			
OTHER ASSESSMENTS																			
Pharmacokinetics ¹⁴	X				X		X		X		X		X		X		X		X
Anti-drug antibodies ¹⁴	X				X		X		X		X		X		X		X		X
CRP ⁶	X				X		X		X		X		X		X		X		X
Fecal calprotectin	X						X				X				X				X
Soluble protein biomarkers in serum ⁹	X						X				X				X				X
Previous and concomitant therapy	X			X	X	X	X	X	X	X	X	X	X	X	X	X	X	X	X
Adverse events ⁸	X		X	X	X	X	X	X	X	X	X	X	X	X	X	X	X	X	X
TRIAL MEDICATION																			
Contact IRT	X ¹⁶	X ¹⁶	X	X	X	X	X	X	X	X	X	X	X	X	X	X	X	X	X
Administration of trial medication ⁷			X	X	X	X	X	X	X	X	X	X	X	X	X	X	X	X	X

**FLOW CHART 1: PATIENTS (1) ROLLING-OVER AT WEEK 26 FROM PRECEDING TRIAL 1311.6
 (WITH CLINICAL RESPONSE BUT NOT REMISSION AT VISIT E1); OR (2) WHO
 MAINTAINED RESPONSE AFTER COMPLETION OF TRIAL 1311.6,
 VISITS 19-EOT**

Trial Period	Treatment period									
	19	20	21	22	23	24	25	26	27	EoT ³
Visit	140	148	156	164	172	180	188	196	204	
Week										
Time window (days)	±7	±7	±7	±7	±7	±7	±7	±7	±7	±7
LABS/SAFETY ASSESSMENTS										
Detailed physical examination										X
Targeted physical examination (incl. vital signs)	X	X	X	X	X	X	X	X	X	
Weight	X	X	X	X	X	X	X	X	X	X
12 Lead Resting-ECG		X						X		X
Urine Pregnancy test ⁴	X	X	X	X	X	X	X	X	X	
Laboratory tests (serum chemistry, hematology, urinalysis) ⁹	X	X	X	X	X	X	X	X	X	X
QuantiFERON-TB Gold In-Tube test ⁵		X					X			
EFFICACY ASSESSMENTS										
Crohn's Disease Activity Index (CDAI), PRO-2	X	X	X	X	X	X	X	X	X	X
Review patient diary	X	X	X	X	X	X	X	X	X	X
Fistula exam	X	X	X	X	X	X	X	X	X	X
Inflammatory Bowel Disease Questionnaire (IBDQ) ¹²		X			X			X		X
Ileocolonoscopy (CDEIS)			X						X ¹⁰	X ¹¹
OTHER ASSESSMENTS										
Pharmacokinetics ¹³	X		X		X		X		X	X
Anti-drug antibodies ¹³	X		X		X		X		X	X
CRP ⁹	X		X	X		X	X		X	X
Fecal calprotectin			X				X		X	X
Soluble protein biomarkers in serum ⁹			X				X		X	X
Previous and concomitant therapy	X	X	X	X	X	X	X	X	X	X
Adverse events ⁶	X	X	X	X	X	X	X	X	X	X
TRIAL MEDICATION										
Contact IRT	X	X	X	X	X	X	X	X	X	X ⁸
Administration of trial medication ⁷	X	X	X	X	X	X	X	X	X	

1. Visit 1 of this LT extension study should preferably be performed in one visit combined with the last visit of the preceding trial 1311.6 or during the interim period of maximum 5 days after completion of the last visit in 1311.6. If an EoT colonoscopy has not been performed during E1 within 1311.6, it must be performed between V1 and V2 in 1311.20/M15-989.
2. Assessments performed at the last visit in the previous trial do not have to be repeated at visit 1 in this trial. Assessments scheduled but not performed at the last visit in the previous trial should be repeated at Visit 1 in this trial, and the results entered into the CRFs of both trials 1311.6 and 1311.20/M15-989.
3. For patients who discontinue study medication before scheduled EoT visit, an early EoT visit should be performed. After last dose of study medication, a 140 day follow-up call should be scheduled. Upon EC/CA approvals of Study M16-000 protocol amendment 4, patients receiving treatment in M15-989 will have the option to enroll into M16-000 Sub-Study 3 after completing the EoT visit.
4. Must be performed at Visit 1 and starting from Visit 2 prior to each study drug administration in females of childbearing potential. In case of positive result, serum pregnancy test will be performed. Study drug will only be administered if pregnancy is ruled out.
5. Positive QuantiFERON-TB Gold In-Tube tests need not to be repeated. If TB or infection is suspected at any time during the study, a routine work up including chest x-ray and a QuantiFERON-TB Gold In-Tube test or an infection assessment must be performed at investigator's discretion and according to local guidelines.
6. Assessment of AE after subcutaneous injections will also include assessment of local tolerability. The assessment of local tolerability should be done just before the patient leaves the investigator site.
7. All assessments are to be completed prior to study drug administration, unless otherwise specified.
8. An end of trial call should be performed for both patients that agree to enroll into M16-000 Sub-Study 3 OLE or those that do not choose to participate.
9. For details of laboratory tests see [Section 5.2.3](#), [Table 5.2.3:1](#) and [Table 5.2.3:2](#).
10. Every effort should be made for the patient to perform a final ileocolonoscopy at the study visit where the last dose of study medication is administered. For patients with early EoT, every effort should be made to perform a final ileocolonoscopy within 2 weeks following the early EoT visit.
11. Colonoscopy is not to be repeated if done at preceding visit.
12. IBDQ should be completed before site staff interaction and study drug administration.
13. Blood samples for PK and ADA will be drawn BEFORE drug administration, i.e. pre-dose, whenever visits coincide.
14. Visit 1.1 is applicable only for those patients that had visit E1 more than 5 days before Visit 1. Visit 1.1 can be performed by phone, fax or email.
15. IRT has to be called only once at V1 or V1.1 after assessment if s.c or i.v. re-induction is needed.
16. In case patient had visit E1 less than 5 days before Visit 1, CDAI assessment and new patient diary dispense should be done at Visit 1.

**FLOW CHART 2: PATIENTS (1) ROLLING-OVER AT WEEK 52 FROM PRECEDING TRIAL 1311.6
 (WITH CLINICAL RESPONSE OR REMISSION AT VISIT E5) VISITS 1-18**

Trial Period	Screening		Treatment period																
	1 ¹²	1.1 ¹⁵	2	3	4	5	6	7	8	9	10	11	12	13	14	15	16	17	18
Visit		1	6	14	22	30	38	46	54	62	70	78	86	94	102	110	118	126	134
Week	0		6	14	22	30	38	46	54	62	70	78	86	94	102	110	118	126	134
Time window (days)	+5	+5	± 7	± 7	± 7	± 7	± 7	± 7	± 7	± 7	± 7	± 7	± 7	± 7	± 7	± 7	± 7	± 7	± 7
Informed consent	X																		
Assessment of eligibility	X																		
LABS/SAFETY ASSESSMENTS																			
Detailed physical examination	X																		
Targeted physical examination (incl. vital signs)			X	X	X	X	X	X	X	X	X	X	X	X	X	X	X	X	X
Weight	X		X	X	X	X	X	X	X	X	X	X	X	X	X	X	X	X	X
12 Lead Resting-ECG	X									X									
Urine Pregnancy test ⁴	X		X	X	X	X	X	X	X	X	X	X	X	X	X	X	X	X	X
Laboratory tests (serum chemistry, hematology, urinalysis) ⁹	X		X	X	X	X	X	X	X	X	X	X	X	X	X	X	X	X	X
QuantiFERON-TB Gold In-Tube test ⁵	X								X						X				
EFFICACY ASSESSMENTS																			
Dispense patient diary for screening ¹⁵	X																		
Crohn's Disease Activity Index (CDAI), PRO-2	X ¹⁶	X	X	X	X	X	X	X	X	X	X	X	X	X	X	X	X	X	X
Review patient diary	X ¹⁶	X	X	X	X	X	X	X	X	X	X	X	X	X	X	X	X	X	X
Fistula exam	X		X	X	X	X	X	X	X	X	X	X	X	X	X	X	X	X	X
Inflammatory Bowel Disease Questionnaire (IBDQ) ¹³			X			X			X			X			X			X	
Ileocolonoscopy (CDEIS)	X ¹								X								X		
OTHER ASSESSMENTS																			
Pharmacokinetics ¹⁴	X			X		X		X		X		X		X		X		X	
Anti-drug antibodies ¹⁴	X			X		X		X		X		X		X		X		X	
CRP ⁹	X			X		X		X		X		X		X		X		X	
Fecal calprotectin	X					X				X				X				X	
Soluble protein biomarkers in serum ⁹	X					X				X				X				X	
Previous and concomitant therapy	X		X	X	X	X	X	X	X	X	X	X	X	X	X	X	X	X	X
Adverse events ⁶	X		X	X	X	X	X	X	X	X	X	X	X	X	X	X	X	X	X
TRIAL MEDICATION																			
Contact IRT	X		X	X	X	X	X	X	X	X	X	X	X	X	X	X	X	X	X
Administration of trial medication ⁷			X	X	X	X	X	X	X	X	X	X	X	X	X	X	X	X	X

**FLOW CHART 2: PATIENTS (1) ROLLING-OVER AT WEEK 52 FROM PRECEDING TRIAL 1311.6
 (WITH CLINICAL RESPONSE OR REMISSION AT VISIT E5); VISITS 19-EOT**

Trial Period	Treatment period									
	19	20	21	22	23	24	25	26	27	EoT ³
Visit	142	150	158	166	174	182	190	198	206	
Week										
Time window (days)	±7	±7	±7	±7	±7	±7	±7	±7	±7	±7
LABS/SAFETY ASSESSMENTS										
Detailed physical examination										X
Targeted physical examination (incl. vital signs)	X	X	X	X	X	X	X	X	X	
Weight	X	X	X	X	X	X	X	X	X	X
12 Lead Resting-ECG		X						X		X
Urine Pregnancy test ⁴	X	X	X	X	X	X	X	X	X	
Laboratory tests (serum chemistry, hematology, urinalysis) ⁵	X	X	X	X	X	X	X	X	X	X
QuantifERON-TB Gold In-Tube test ⁶		X						X		
EFFICACY ASSESSMENTS										
Crohn's Disease Activity Index (CDAI), PRO-2	X	X	X	X	X	X	X	X	X	X
Review patient diary	X	X	X	X	X	X	X	X	X	X
OTHER ASSESSMENTS										
Fistula exam	X	X	X	X	X	X	X	X	X	X
Inflammatory Bowel Disease Questionnaire (IBDQ) ¹²		X			X			X		X
Ileocolonoscopy (CDEIS)			X						X ¹⁰	X ¹¹
Pharmacokinetics ¹³	X		X		X		X		X	X
Anti-drug antibodies ¹³	X		X		X		X		X	X
CRP ⁹	X		X	X		X	X		X	X
Fecal calprotectin			X				X		X	X
Soluble protein biomarkers in serum ⁹			X				X		X	X
Previous and concomitant therapy	X	X	X	X	X	X	X	X	X	X
Adverse events ⁶	X	X	X	X	X	X	X	X	X	X
TRIAL MEDICATION										
Contact IRT	X	X	X	X	X	X	X	X	X	X ⁸
Administration of trial medication ⁷	X	X	X	X	X	X	X	X	X	X

1. Visit 1 of this LT extension study should preferably be performed in one visit combined with the last visit of the preceding trial 1311.6 or during the interim period of maximum 5 days after completion of the last visit in 1311.6. If an EoT colonoscopy has not been performed during E5 within 1311.6, it must be performed between V1 and V2 in 1311.20/M15-989.
2. Assessments performed at the last visit in the previous trial do not have to be repeated at visit 1 in this trial. Assessments scheduled but not performed at the last visit in the previous trial should be repeated at visit 1 in this trial, and the results entered into the CRFs of both trials 1311.6 and 1311.20/M15-989.
3. For patients who discontinue study medication before scheduled EoT visit, an early EoT visit should be performed. After last dose of study medication, a 140 day follow-up call should be scheduled. Upon EC/CA approvals of Study M16-000 protocol amendment 4, patients receiving treatment in M15-989 will have the option to enroll into M16-000 Sub-Study 3 after completing the EoT visit.
4. Must be performed at Visit 1 and starting from Visit 2 prior to each study drug administration in females of childbearing potential. In case of positive result, serum pregnancy test will be performed. Study drug will only be administered if pregnancy is ruled out.
5. Positive QuantiFERON-TB Gold In-Tube tests need not to be repeated. If TB or infection is suspected at any time during the study, a routine work up including chest x-ray and a QuantiFERON-TB Gold In-Tube test or an infection assessment must be performed at investigator's discretion and according to local guidelines.
6. Assessment of AE after subcutaneous injections will also include assessment of local tolerability. The assessment of local tolerability should be done just before the patient leaves the investigator site.
7. All assessments are to be completed prior to study drug administration, unless otherwise specified.
8. An end of trial call should be performed for both patients that agree to enroll into M16-000 Sub-Study 3 OLE or those that do not choose to participate.
9. For details of laboratory tests see [Section 5.2.3](#), [Table 5.2.3:1](#) and [Table 5.2.3:2](#)
10. Every effort should be made for the patient to perform a final ileocolonoscopy at the study visit where the last dose of study medication is administered. For patients with early EoT, every effort should be made to perform a final ileocolonoscopy within 2 weeks following the early EoT visit.
11. Colonoscopy is not to be repeated if done at preceding visit.
12. IBDQ should be completed before site staff interaction and study drug administration.
13. Blood samples for PK and ADA will be drawn BEFORE drug administration, i.e. pre-dose, whenever the visits coincide.
14. Visit 1.1 is applicable only for those patients that had visit E5 more than 5 days before Visit 1. Visit 1.1 can be performed by phone, fax or email.
15. In case patient had visit E5 less than 5 days before Visit 1, CDAI assessment and new patient diary dispense should be done at Visit 1.

**FLOW CHART 3: PATIENTS ROLLING-OVER WHO HAVE LOST RESPONSE OR REMISSION
AFTER COMPLETION OF TRIAL 1311.6 EITHER AT VISIT E1 OR E5, VISITS 1-18**

Trial Period	Screening		Re-induction				Treatment period														
	1 ^{1,2}	1,1 ¹⁶	2	3	4	5	6	7	8	9	10	11	12	13	14	15	16	17	18	19	
Visit	0	1	4	8	12	16	24	32	40	48	56	64	72	80	88	96	104	112	120	128	
Week	+5	+5	± 7	± 5	± 5	± 7	± 7	± 7	± 7	± 7	± 7	± 7	± 7	± 7	± 7	± 7	± 7	± 7	± 7	± 7	
Time window (days)																					
Informed consent	X																				
Assessment of eligibility	X						X ¹⁵														
LABS/SAFETY ASSESSMENTS																					
Detailed physical examination	X																				
Targeted physical examination (incl. vital signs)						X	X	X	X	X	X	X	X	X	X	X	X	X	X	X	
Weight	X					X	X	X	X	X	X	X	X	X	X	X	X	X	X	X	
12 Lead Resting-ECG	X																			X	
Urine Pregnancy test ⁴	X					X	X	X	X	X	X	X	X	X	X	X	X	X	X	X	
Laboratory tests (serum chemistry, hematology, urinalysis) ⁹	X					X	X	X	X	X	X	X	X	X	X	X	X	X	X	X	
QuantiFERON-TB Gold In-Tube test ⁵	X										X						X				
EFFICACY ASSESSMENTS																					
Dispense patient diary for screening	X																				
Crohn's Disease Activity Index (CDAI), PRO-2		X	X	X	X	X	X	X	X	X	X	X	X	X	X	X	X	X	X	X	
Review patient diary	X	X	X	X	X	X	X	X	X	X	X	X	X	X	X	X	X	X	X	X	
Fistula exam	X	X	X	X	X	X	X	X	X	X	X	X	X	X	X	X	X	X	X	X	
Inflammatory Bowel Disease Questionnaire (IBDQ) ¹³						X			X			X			X			X			
Ileocolonoscopy (CDEIS)	X ¹											X								X	
OTHER ASSESSMENTS																					
Pharmacokinetics ¹⁴	X								X	X	X	X	X	X	X	X	X	X	X	X	
Anti-drug antibodies ¹⁴	X								X	X	X	X	X	X	X	X	X	X	X	X	
CRP ⁹	X								X	X	X	X	X	X	X	X	X	X	X	X	
Fecal calprotectin	X								X	X										X	
Soluble protein biomarkers in serum ⁹	X								X	X										X	
Previous and concomitant therapy	X		X	X	X	X	X	X	X	X	X	X	X	X	X	X	X	X	X	X	
Adverse events ⁵	X	X	X	X	X	X	X	X	X	X	X	X	X	X	X	X	X	X	X	X	
TRIAL MEDICATION																					
Contact IRT	X	X ¹⁷	X	X	X	X	X	X	X	X	X	X	X	X	X	X	X	X	X	X	
Administration of trial i.v. medication ⁷			X	X	X																
Administration of trial s.c. medication ⁷						X	X	X	X	X	X	X	X	X	X	X	X	X	X	X	

**FLOW CHART 3: PATIENTS ROLLING-OVER WHO HAVE LOST RESPONSE OR REMISSION
AFTER COMPLETION OF TRIAL 1311.6 EITHER AT VISIT E1 OR E5, VISITS 19-EOT**

Trial Period	Treatment period											
	20	219	22	23	24	25	26	27	28	29	30	EoT ³
Visit	136	144	152	160	168	176	184	192	200	208	216	
Week												
Time window (days)	±7	±7	±7	±7	±7	±7	±7	±7	±7	±7	±7	±7
LABS/SAFETY ASSESSMENTS												
Detailed physical examination												X
Targeted physical examination (incl. vital signs)	X	X	X	X	X	X	X	X	X	X	X	
Weight	X	X	X	X	X	X	X	X	X	X	X	X
12 Lead Resting-ECG				X								X
Urine Pregnancy test ⁴	X	X	X	X	X	X	X	X	X	X	X	
Laboratory tests (serum chemistry, hematology, urinalysis) ⁹	X	X	X	X	X	X	X	X	X	X	X	X
QuantiFERON-TB Gold In-Tube test ⁵		X						X				
EFFICACY ASSESSMENTS												
Crohn's Disease Activity Index (CDAI), PRO-2	X	X	X	X	X	X	X	X	X	X	X	X
Review patient diary	X	X	X	X	X	X	X	X	X	X	X	X
Fistula exam	X	X	X	X	X	X	X	X	X	X	X	X
Inflammatory Bowel Disease Questionnaire (IBDQ) ¹²	X			X			X			X		X
Ileocolonoscopy (CDEIS)					X						X ¹⁰	X ¹¹
OTHER ASSESSMENTS												
Pharmacokinetics ¹³	X		X		X		X		X		X	X
Anti-drug antibodies ¹³	X		X		X		X		X		X	X
CRP ⁹	X	X	X		X	X		X	X		X	X
Fecal calprotectin	X				X				X		X	X
Soluble protein biomarkers in serum ⁹	X				X				X		X	X
Previous and concomitant therapy	X	X	X	X	X	X	X	X	X	X	X	X
Adverse events ⁶	X	X	X	X	X	X	X	X	X	X	X	X
TRIAL MEDICATION												
Contact IRT	X	X	X	X	X	X	X	X	X	X	X	X ⁸
Administration of trial i.v. medication ⁷												
Administration of trial s.c. medication ⁷	X	X	X	X	X	X	X	X	X	X	X	

1. If an EoT colonoscopy has not been performed during E1/E5 within 1311.6, or if the patient had a treatment interruption followed by a clinical relapse, it must be performed between V1 and V2 in 1311.20/M15-989.
2. Assessments performed at visit E1/E5 in the previous trial do not have to be repeated at Visit 1 in this trial. Assessments scheduled but not performed at Visit E1/E5 in the previous trial should be repeated at visit 1 in this trial, and the results entered into the CRFs of both trials, 1311.6 and 1311.20/M15-989.
3. For patients who discontinue study medication before scheduled EoT visit, an early EoT visit should be performed. After last dose of study medication, a 140 day follow-up call should be scheduled. Upon EC/CIA approvals of Study M16-000 protocol amendment 4, patients receiving treatment in M15-989 will have the option to enroll into M16-000 Sub-Study 3 after completing the EoT visit.
4. Must be performed at Visit 1 and starting from Visit 2 prior to each study drug administration in females of childbearing potential. In case of positive result, serum pregnancy test will be performed. Study drug will only be administered if pregnancy is ruled out.
5. Positive QuantiFERON-TB Gold In-Tube tests need not to be repeated. If TB or infection is suspected at any time during the study, a routine work up including chest x-ray and a QuantiFERON-TB Gold In-Tube test or an infection assessment must be performed at investigator's discretion and according to local guidelines.
6. Assessment of AE after intravenous infusions and subcutaneous injections will also include assessment of local tolerability. The assessment of local tolerability should be done just before the patient leaves the investigator site.
7. All assessments are to be completed prior to study drug administration, unless otherwise specified.
8. An end of trial call should be performed for both patients that agree to enroll into M16-000 Sub-Study 3 OLE or those that do not choose to participate.
9. For details of laboratory tests see [Section 5.2.3](#), [Table 5.2.3.1](#) and [Table 5.2.3.2](#).
10. Every effort should be made for the patient to perform a final ileocolonoscopy at the study visit where the last dose of study medication is administered. For patients with early EoT, every effort should be made to perform a final ileocolonoscopy within 2 weeks following the early EoT visit.
11. Colonoscopy is not to be repeated if done at preceding visit.
12. IBDQ should be completed before site staff interaction and study drug administration.
13. Blood samples for PK and ADA will be drawn BEFORE drug administration, i.e. pre-dose, whenever the visits coincide.
14. Clinical response or remission will be compared to 1311.6 baseline (Visit 2), to continue SC medication patients should have response.
15. Visit can be performed by phone, fax or email.
16. IRT has to be called only once at V1 or V1.1 after assessment if s.c or i.v. re-induction is needed.

4.2.2 Variables Used for Stratification of Randomization

Not applicable.

4.3 Endpoints

4.3.1 Primary Efficacy Endpoint

There is no primary efficacy endpoint specified.

4.3.2 Secondary Efficacy Endpoint

- Clinical remission by visit defined as a CDAI < 150.
- Clinical response by visit, defined by either a CDAI < 150 or a CDAI reduction from baseline of at least 100 points.
- PRO-2 remission by visit, defined by a PRO-2 score < 75
- PRO-2 response by visit, defined as a decrease from baseline of 50 points or more.
- CDEIS remission, defined as a score of 4 or less, by visit (for patients with initial isolated ileitis a score of 2 or less)
- CDEIS response, defined as a score of 7 or less, by visit (for patients with initial isolated ileitis > 50% reduction from baseline).

- Mucosal healing, using CDEIS defined as the absence of mucosal ulceration, i.e., ulceration sub-score (deep ulceration, superficial ulceration, ulcerated stenosis) is 0, by visit.
- Deep remission, defined as clinical remission and CDEIS remission by visit.
- IBDQ remission (IBDQ total score > 170 points) by visit.
- IBDQ response (increase in IBDQ total score > 16 points from baseline) by visit.
- Change from baseline in CDAI by visit.
- Change from baseline in PRO-2 scores by visit.
- Change from baseline in CDEIS by visit.
- Change from baseline in SES-CD by visit.
- Change from baseline in stool frequency (SF) by visit based on patient diary.
- Change from baseline in abdominal pain (AP) score by visit based on patient diary.
- Change from baseline in IBDQ total scores by visit.
- Change from baseline in IBDQ domain scores by visit.
- Change from baseline in hs-CRP by visit.
- Change from baseline in fecal calprotectin profile by visit.

Note: For the composite endpoints such as deep remission, please refer to Appendix 12.9 for detailed analysis convention.

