4.3.3 Exploratory Efficacy Endpoint

The following endpoints will be summarized in subjects with baseline SF ≥ 4 or AP ≥ 2 , and baseline SES-CD, excluding the presence of narrowing component, ≥ 6 (≥ 4 for subjects with initial isolated ileitis).

- Proportion of subjects with average daily SF ≤ 2.8 and not worse than baseline and average daily AP score ≤ 1 and not worse than baseline, by visit.
- Proportion of subjects with decreasing in SES-CD $> 50\%$ from baseline (or for a baseline SES-CD of 4, at least a 2 point reduction from Baseline), by visit.

- Proportion of subjects with $\geq 60\%$ decrease in average daily SF and/or $\geq 35\%$ decrease in average daily AP score and both not worse than baseline, and/or achievement of average daily SF ≤ 2.8 and AP ≤ 1 and both not worse than baseline, by visit.
- Proportion of subjects with SES-CD ulcerated surface subscore of 0 in subjects with SES-CD ulcerated surface subscore ≥ 1 at baseline, by visit.
- Proportion of subjects with SES-CD ≤ 4 and at least a 2 point reduction versus baseline and no subscore greater than 1 in any individual variable, by visit.
- Proportion of subjects who discontinued corticosteroid use for at least 90 days before or at visit and achieved average daily SF ≤ 2.8 and AP ≤ 1 and both not worse than baseline in subjects taking steroids at baseline, by visit.

Note: To summarize discontinuing corticosteroid use for at least 90 days before or at visit in Study M15-989, the concomitant medication records from the feeder Study M15-993 need to be taken into account.

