6.0 Analysis Conventions

6.1 Definition of Baseline

Efficacy analysis:

For efficacy analysis, the baseline is defined as the last measurement prior to the first dose of the study drug in the feeder Study M15-993 (1311.6).

Safety analysis:

For safety analyses, the baseline is defined as the last measurement prior to the first dose of risankizumab in the feeder Study M15-993 (1311.6).

Demographics and Baseline Characteristics:

For Demographics and Baseline Characteristics, the data will be from the baseline of the feeder Study M15-993 (1311.6).

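### CDEIS mucosal healing (SAP 4.3.2) can count patients who had no ulcers at the 1311.6 baseline, whereas the SAP's SES-CD counterpart excludes them

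*SAP*

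**What the plan says.** The secondary endpoint in SAP 4.3.2 is "Mucosal healing, using CDEIS defined as the absence of mucosal ulceration, i.e., ulceration sub-score (deep ulceration, superficial ulceration, ulcerated stenosis) is 0, by visit". Protocol 5.1.1 has the same concept, absence of ulceration, also without a baseline condition. SAP 5.1.1 uses the ITT set for efficacy: everyone with at least one dose in this study, with IV and SC subsets for by-period analyses. SAP 6.1 fixes the reference point: "For efficacy analysis, the baseline is defined as the last measurement prior to the first dose of the study drug in the feeder Study M15-993".

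The exploratory SES-CD endpoint in SAP 4.3.3 is built differently: "Proportion of subjects with SES-CD ulcerated surface subscore of 0 in subjects with SES-CD ulcerated surface subscore ≥ 1 at baseline, by visit". It is also confined to the subgroup with active disease at baseline that opens that section.

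For the table note, SAP 4.3.2 pairs "PRO-2 remission by visit, defined by a PRO-2 score < 75" with "PRO-2 response by visit, defined as a decrease from baseline of 50 points or more". The clinical pair has a remission limb: "Clinical response by visit, defined by either a CDAI < 150 or a CDAI reduction from baseline of at least 100 points". In isolated ileitis, CDEIS remission is a score of at most 2, and response is a reduction of more than 50%. IBDQ remission is a total above 170, and response is a rise of more than 16 points.

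**The concern.** Healing implies that there was something to heal. As written, the mucosal healing numerator can include patients whose ulceration sub-score was already 0 before their first dose in the feeder trial. They add to the count without any change on treatment. The SAP takes account of this for SES-CD ulceration but not for the CDEIS endpoint, which ranks higher in its own list. A reader who sets the two ulcer endpoints side by side would be comparing different denominators.

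The study is descriptive, so no test or error rate is affected. What is at stake is the meaning of a reported proportion in a study whose efficacy output is a set of by-visit proportions.

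A smaller matter concerns pairs of endpoints. Three response definitions do not contain their remission counterpart, so a remission rate could exceed the matching response rate and puzzle a reader.

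**Working it through.** The plan gives no rate or sample size for these endpoints, so there is no figure to reproduce. The check is of the definitions and their arithmetic.

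**1. Can a patient have active endoscopic disease without ulcers?** In SAP 12.3 the CDEIS also scores surface involved by disease (0 to 10 per segment, averaged over the segments explored) and adds 3 for a non-ulcerated stenosis.
- All five segments fully involved, no ulcers: (5 × 10)/5 + 3 = 13.
- Ileum only, five segments explored, no ulcers: 10/5 + 3 = 5.

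An active but ulcer-free baseline is therefore arithmetically possible. Nothing in SAP 5.1.1, 9.1.2, 12.3 or 12.9 removes such a patient.

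**2. Effect on the reported rate.** Let *f* be the share ulcer-free at the 1311.6 baseline, *p* the healing rate among patients with ulcers at baseline, and *s* the share of the ulcer-free group counted as achieved at the visit.

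Reported rate = f × s + (1 − f) × p, so the excess over *p* is f × (s − p).

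Assumed: p = 0.30 and s = 1. The denominator uses the planned figure of about 60 patients.

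| f (assumed) | Reported rate | Restricted rate | Restricted denominator |
|---|---|---|---|
| 0 | 30% | 30% | 60 |
| 0.05 | 0.05 + 0.95 × 0.30 = 33.5% (34%) | 30% | 60 − 3 = 57 |
| 0.10 | 0.10 + 0.90 × 0.30 = 37% | 30% | 60 − 6 = 54 |
| 0.20 | 0.20 + 0.80 × 0.30 = 44% | 30% | 60 − 12 = 48 |

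Setting s = 1 gives the largest excess for each *f* at this *p*. Under the non-responder imputation in SAP 9.1.2, a missing visit counts as not achieved, which lowers *s*.

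**3. Which remission and response pairs are nested?**
- *PRO-2.* By SAP 12.2, in daily means, PRO-2 = 2 × 7 × SF + 5 × 7 × AP = 14 SF + 35 AP. Remission without response needs a follow-up score below 75 and above baseline − 50. That is possible only if baseline − 50 < 75, so baseline < 125. Example: SF 4, AP 1 gives 56 + 35 = 91. SF 2.8, AP 1 gives 39.2 + 35 = 74.2. The patient is in remission after a fall of 16.8.
- *CDEIS in isolated ileitis.* From 4 to 2 is remission, but the reduction is (4 − 2)/4 = 50%, not more than 50%.
- *IBDQ.* From 160 to 172 is remission, but the rise is 12, not more than 16.
- *Nested pairs.* CDAI is nested through its remission limb. CDEIS outside isolated ileitis is nested because a score of at most 4 is also at most 7.

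**The case against.** The strongest defence on mucosal healing is that the endpoint is openly defined as absence of ulceration, the protocol agrees with the SAP, and the effect may be nil. How many patients were ulcer-free at baseline depends on the endoscopic entry criteria of 1311.6, which the documents do not give. If that trial required ulcers, the excess is zero. The SAP also already reports one ulcer endpoint restricted to patients ulcerated at baseline. Most of this stands, and it limits the size of the point. It does not answer the difference between the two ulcer endpoints: the restricted one uses another index and sits inside an exploratory subgroup, so it does not give the CDEIS healing rate among all patients with baseline ulcers.

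On PRO-2, a reader might infer that response is misclassified or biased downwards, and that it should be redefined to include a score below 75. The documents do not support that. A fall of 16.8 points is correctly not a 50-point fall. No section requires response to contain remission, and IBDQ is not nested either. The added limb would also create the very problem raised for mucosal healing: a patient with baseline SF 4 and AP 0 (14 × 4 = 56) would be a responder with no change at all. The same applies to an ileitis patient who starts at CDEIS 2.

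A reader might also take the share of patients with a baseline PRO-2 below 125 as the share affected. It is not, since discordance also needs a follow-up score between baseline − 50 and 75. The documents give no baseline PRO-2 distribution from which to compute either share.

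**Conclusion.** The point holds for mucosal healing and is minor. The definition lets patients with no ulceration at the 1311.6 baseline count as healed, and the SAP's own SES-CD endpoint shows the better construction. It is not a departure of the SAP from the protocol.

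The excess is f × (s − p). With p = 30% and every ulcer-free patient staying so, it is 0, 3.5, 7 or 14 percentage points for f = 0, 5, 10 or 20%. Both *f* and *p* are assumptions, and *f* may be zero. A reader should not infer that the reported rate is known to be inflated.

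For PRO-2 response, isolated-ileitis CDEIS response and IBDQ response, the finding is only that they are not nested with the matching remission endpoint. That calls for a note to the tables, not a change of definition.

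**What to change.** - In SAP 4.3.2, report mucosal healing by visit among patients with a CDEIS ulceration sub-score above 0 at the 1311.6 baseline. Tie this to the SAP 6.1 baseline explicitly, because Protocol 3.1 also calls the last 1311.6 colonoscopy a baseline for this study.
- Keep the protocol-defined all-patient row, labelled 'absence of ulceration', and state how many patients were ulcer-free at the 1311.6 baseline. That number shows at once whether the issue matters.
- Add a note to the PRO-2, CDEIS and IBDQ tables: PRO-2 response, CDEIS response in isolated ileitis, and IBDQ response do not contain the matching remission endpoint, so the two rates are not nested. Leave the protocol definitions as they are.

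The cost is SAP wording, one extra row and a footnote. The restricted row has a smaller denominator and so a less precise percentage. No new data are needed beyond the baseline CDEIS components from the feeder trial.
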